Analysis of Primary Endpoint: The primary efficacy endpoint for this study is the change in the TTS of the YGTSS from baseline to week 8 between high-dose TEV-50717-treated and placebo-treated patients. The primary analysis will be a mixed-model repeated-measures model with the change in the TTS as the dependent variable. The model will include fixed effects for treatment group, week (3 levels: weeks 2, 4, and 8), and the treatment group-by-week interaction. The baseline TTS, region, and age group at baseline (2 levels: 6 to 11 years, 12 to 16 years) will be included as covariates. The unstructured covariance matrix for repeated observations within patients will be used. The least squares means of the change in TTS from baseline at week 8 will be compared between the high-dose treatment arm and the placebo arm using a 2-sided test at the $\alpha = 0.05$ level of significance. In addition, actual values and changes in the TTS from baseline to each visit will be summarized using descriptive statistics.

Analysis of Key Secondary Endpoints: A hierarchical (fixed-sequence) testing approach will be used for the analysis of the key secondary endpoints. If an endpoint is not statistically significant, confirmatory hypothesis testing will not be carried out on the remaining hypotheses, and remaining hypotheses will be considered exploratory rather than confirmatory. The following analyses of key secondary endpoints will be conducted:

1. The change from baseline to week 8 in TS-CGI will be analyzed using a similar model as the primary analysis; however, instead of change in YGTSS TTS as the dependent variable and baseline YGTSS TTS as a covariate, the corresponding TS-CGI values will be used. The comparison between high-dose TEV-50717 and placebo will be tested.
2. Using the same model as for the primary analysis, the comparison between the change in the TTS of the YGTSS from baseline to week 8 for low-dose TEV-50717 and placebo will be tested.
3. Using the same model as described in endpoint #1 above for TS-CGI, the comparison between the change in the TS-CGI values from baseline to week 8 for low-dose TEV-50717 and placebo will be tested.
4. The change from baseline to week 8 in TS-PGII will be analyzed using a Cochran-Mantel-Haenszel row mean score test with modified ridit scoring controlling for age group. The comparison between high-dose TEV-50717 and placebo will be tested.

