5. Using the same model as described in endpoint #4 above for TS-PGII, the comparison between the change in the TS-PGII values from baseline to week 8 for low-dose TEV-50717 and placebo will be tested.
6. The change from baseline to week 8 in C&A-GTS-QOL ADL subscale will be analyzed using a similar model as the primary analysis; however, instead of change in YGTSS TTS as the dependent variable and baseline YGTSS TTS as a covariate, the corresponding C&A-GTS-QOL ADL subscale values will be used. The comparison between high-dose TEV-50717 and placebo will be tested.
7. Using the same model as described in endpoint #6 above for C&A-GTS-QOL ADL subscale, the comparison between the change in the C&A-GTS-QOL ADL subscale scores from baseline to week 8 for low-dose TEV-50717 and placebo will be tested.

Exploratory Analyses:

[REDACTED]

[REDACTED]

[REDACTED]

[REDACTED]

[REDACTED]

[REDACTED]

[REDACTED]

[REDACTED]

[REDACTED]

[REDACTED]

Multiple Comparisons and Multiplicity: The hierarchical testing method will be used to maintain the experiment-wise type I error of 5% level for the primary and key secondary analyses. The primary efficacy endpoint will first be tested at the 5% type I error level. If the p-value of the primary analysis is ≤ 0.05 , the secondary hypotheses will be tested in the order listed for the analysis of key secondary endpoints until either an analysis produces a p-value > 0.05 or all analyses result in a p-value ≤ 0.05 .

Analysis of Pharmacokinetic Endpoint: Samples collected for pharmacokinetic analysis will be quantified for α -HTBZ and β -HTBZ metabolite plasma concentrations and will be pooled with previous data and analyzed using population pharmacokinetic techniques. Analysis methods will be detailed in a separate population pharmacokinetic analysis plan. Exploratory pharmacokinetic/pharmacodynamic (PD) analysis may be performed on PD/safety endpoints.

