3. STUDY DESIGN

3.1. General Study Design and Study Schematic Diagram

This is a Phase 3, randomized, double-blind, placebo-controlled, 8-week treatment study in which patients with tics associated with TS will be invited to participate. Patients will be randomized to low-dose TEV-50717, high-dose TEV-50717, or placebo (1:1:1). The target dose for each patient receiving TEV-50717 will be based on the group to which they are randomized, body weight at baseline, and cytochrome P450 2D6 (CYP2D6) impairment status. Patients will be classified as CYP2D6 impaired if they are receiving a strong CYP2D6 inhibitor or are a CYP2D6 poor metabolizer based on blinded assessment of CYP2D6 genotype at baseline, which will be used only by IRT for randomization into the study.

Prescreening period (up to 3 months before baseline): For patients who require discontinuation of certain prohibited concomitant medications 3 months before baseline (depot neuroleptics, botulinum toxin, or tetrabenazine), informed consent/assent, depending on the child's age, as appropriate, should be obtained prior to discontinuing the prohibited medication.

Screening period (up to 31 days): After informed consent/assent, depending on the child's age, as appropriate, is obtained, patients who are stable from a medical and psychiatric standpoint will undergo a screening evaluation, including medical history, physical and neurological examination, laboratory testing, and 12-lead ECG, along with rating scales to assess severity, frequency, and impairment of tics and comorbid TS symptoms and behavioral status. The Mini International Neuropsychiatric Interview for Children and Adolescents, or MINI Kid, is a short questionnaire (largely yes/no questions) to screen for clinically significant underlying psychiatric illness that may affect the subject's eligibility. The assessment will focus on detecting major depression, mania/hypomania, obsessive/compulsive disorder, alcohol and substance abuse, attention deficit hyperactivity and conduct disorders, and psychotic disorders.

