9.1. Sample Size and Power Considerations

It is estimated that approximately 50 patients per arm will enable a power of at least 90% to detect a beneficial standardized effect of 68% or more when the TEV-50717 arm is compared to placebo (difference of 6.5 in the change from baseline to week 8 in TTS, assuming a standard deviation of 9.5 in each arm) in a 2-sided type I error rate of 5% after accounting for potential dropouts.

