8.3.1. Secondary Efficacy Analysis

8.3.1.1. Analysis of the change in the TS-CGI from baseline to Week 8

The change in the TS-CGI score from baseline to Week 8 (1st and 3rd secondary endpoints) will be analyzed in the same fashion as the primary analysis in Section 8.2.1, with the exception that the baseline value of the given endpoint will be included as the covariate.

8.3.1.2. Analysis of the change in the TTS of YGTSS between low-dose TEV-50717-treated patients and placebo-treated patients

The change in the TTS of YGTSS from baseline to Week 8 between low-dose TEV-50717 treated patients and placebo-treated patients (2nd secondary endpoint) will be analyzed as part of Section 8.2.1.

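### The TS-CGI model, which serves the first gate after the primary test, leaves baseline TTS unused; adding it costs one degree of freedom and could bring a small gain in power

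*Protocol*

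**What the plan says.** The primary model (Protocol 9.5.5.1, SAP 8.2.1) is a repeated-measures model for change in TTS with treatment, week and their interaction, adjusted for baseline TTS, region and age group.

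For TS-CGI (key secondaries 1 and 3), Protocol 9.5.5.3 and synopsis item 1 of the key secondary analyses keep that model with one substitution: "instead of change in YGTSS TTS as the dependent variable and baseline YGTSS TTS as a covariate, the corresponding TS-CGI values will be used". For the ADL subscale (key secondaries 6 and 7) the wording is parallel: "the corresponding C&A-GTS-QOL ADL subscale values will be used". SAP 8.3.1.1 and 8.3.1.4 repeat the primary model "with the exception that the baseline value of the given endpoint will be included as the covariate". That is less explicit about whether baseline TTS goes or stays, but read with the protocol it goes. Region and age group remain.

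Testing is in fixed sequence (Protocol 9.5.5.3 and 9.6, SAP 8.3). High-dose TS-CGI comes directly after the primary test. If it fails, six hypotheses become exploratory: low-dose TTS, low-dose TS-CGI, and both doses on TS-PGII and ADL.

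**The concern.** TS-CGI is a single clinician rating with seven levels. TTS sums ten items scored 0 to 5 (SAP 8.1.1), and both are scheduled at the baseline visit. One coarse rating carries measurement error, so a second and finer measure of a related quantity may predict week 8 TS-CGI beyond what baseline TS-CGI already predicts. If it does, leaving it out keeps residual variance that could have been removed.

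The data are already in hand. The modified intent-to-treat set requires a baseline YGTSS (Protocol 9.2.2, SAP 5.4), and entry requires a TTS of at least 20 at baseline. Only a baseline TTS set to missing for missing items would be lost.

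What is at stake is power at the gate. The sample size is justified for TTS alone. No effect, standard deviation or power is stated for TS-CGI, so the documents show no margin at this step.

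**Working it through.** **The plan's own figure.** Protocol 9.1 plans 50 per arm for at least 90% power at a two-sided 5% level, with dropouts allowed for. The effect to be detected is a "difference of 6.5 in the change from baseline to week 8 in TTS"; the SD is taken as 9.5. With 1:1:1 allocation, the number per arm for one pairwise comparison is

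n = 2 × (1.960 + 1.282)² × 9.5² / 6.5² = 44.9, so 45 evaluable per arm.

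An assumed 10% loss gives 45 / 0.90 = 50, so the stated size reproduces. The protocol gives no planning dropout rate; SAP 8.2.2 reports 8% early termination. This calculation is for TTS and says nothing about TS-CGI.

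**Effect of one added covariate.** Let r be the partial correlation of baseline TTS with week 8 TS-CGI given the covariates already in the model. Given the baseline, using the change or the week 8 value makes no difference. Residual variance is multiplied by 1 − r² and the standard error by √(1 − r²). The equivalent number per arm, starting from 50, is 50 / (1 − r²). From an assumed 80% power,

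power = Φ[(1.960 + 0.842) / √(1 − r²) − 1.960].

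| r (assumed) | SE factor | Fall in SE | Equivalent n from 50 | Power from 80% |
|---|---|---|---|---|
| 0.05 | 0.9987 | 0.1% | 50.1 | 80.1% |
| 0.1 | 0.9950 | 0.5% | 50.5 | 80.4% |
| 0.2 | 0.9798 | 2.0% | 52.1 | 81.6% |
| 0.3 | 0.9539 | 4.6% | 54.9 | 83.6% |

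**Cost of the degree of freedom.** With 150 patients and eight between-patient terms (three arms, one baseline, one age-group and three region contrasts), about 142 residual degrees of freedom become 141. At r = 0 the standard error rises by a factor of √(142/141) = 1.0035. Break-even is r = √(1/142) = 0.084. Net of this cost, r = 0.05 gives √(0.9975 × 142/141) = 1.002, a slight loss, and r = 0.3 gives 0.9539 × 1.0035 = 0.957, a fall of 4.3%.

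**Where the range for r comes from.** Suppose baseline TTS has reliability a, TS-CGI has reliability c, the quantity behind TS-CGI correlates ρ with itself over 8 weeks, tic severity and tic impact correlate k, and baseline severity affects later impact only through baseline impact. Then

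r = kρ√(ac)(1 − c) / √[(1 − k²ac)(1 − ρ²c²)].

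Assume a = 0.75 to 0.85, c = 0.5 to 0.7 and ρ = 0.5 to 0.7:

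- k = 1.0: r = 0.17 to 0.32
- k = 0.8: r = 0.11 to 0.23
- k = 0.6: r = 0.08 to 0.16
- k = 0.4: r = 0.05 to 0.10

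Example at k = 1, a = 0.85, c = 0.5, ρ = 0.7: 0.7 × 0.652 × 0.5 / √(0.575 × 0.8775) = 0.228 / 0.710 = 0.32.

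A simulation at k = 1 with the TTS entry floor and wider inputs (a = 0.70 to 0.85, c and ρ each 0.4 to 0.8) gave 0.11 to 0.35. Its top values need ρ = 0.8 as well as k = 1. None of these inputs is in the documents.

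**The case against.** The strongest reply is that nothing is wrong with the planned analysis. Adjusting a change score for its own baseline, with region and age group kept, is the usual choice, and protocol and SAP agree on it. That stands: this is an unused option and not an error. A reader might infer that the TS-CGI test is biased or its error rate compromised. Neither follows, because either choice of pre-randomisation covariate gives a valid test of the same contrast.

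A reader might also infer that a known amount of precision is lost. The documents do not support that, since they give no correlation between baseline TTS and TS-CGI. Moreover, both documents define TS-CGI as the clinician's rating of the impact of tics on quality of life, using all available information. It is not simply a coarse tic-severity score, and the baseline rating may already absorb what the tic items show. The upper part of the range needs severity and impact to be nearly one construct. This stands, and it is why the range starts at 0.05.

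Two further limits stand. The model text lists no baseline-by-week interaction, so one baseline slope serves weeks 2, 4 and 8, and 1 − r² is a ceiling on the gain at week 8. The entry floor of 20 narrows the spread of baseline TTS, which the closed-form values ignore.

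Finally, the parallel ADL wording might suggest that ADL is part of the same gate. It is not. ADL is tested sixth and seventh, and high-dose ADL gates only low-dose ADL.

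**Conclusion.** The point holds for TS-CGI, at modest size. A finer baseline tic score that essentially every analysed patient has is left out of the model for the test that gates low-dose TTS and all later endpoints.

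On assumed partial correlations of 0.05 to 0.3 and an assumed 80% starting power, the gain runs from practically nothing to 3.6 percentage points. The lower end is below break-even once the degree of freedom is counted. The recommendation rests on asymmetry: the worst case is about a 0.35% larger standard error, and the better case helps at the step on which six confirmatory tests depend. For ADL no gain has been quantified.

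**What to change.** Before unblinding, state in SAP 8.3.1.1 that the TS-CGI model keeps baseline TTS as a covariate in addition to baseline TS-CGI, region and age group. Align Protocol 9.5.5.3 item 1 and synopsis item 1. Leave the rest of the model, the contrasts, the testing order and the estimand unchanged. The same sentence would settle whether the SAP replaces or retains baseline TTS.

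The cost is one covariate in SAP text and code, one degree of freedom, and the alignment of the protocol. Protocol 9.11 allows such a change to be recorded in the SAP, where section 12 is the place for it. No new data are needed. Once treatment codes are open, this model should not replace the planned one.

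The same addition to the ADL model (SAP 8.3.1.4) is optional and for precision only; it has no bearing on the gate to the low dose.

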- m. Patient has a QT interval corrected for heart rate using Fridericia's formula (QTcF) interval value >450 msec (males) or >460 msec (females), or >480 msec (with right bundle branch block) on a 12-lead electrocardiogram (ECG) at screening, or requires treatment with drugs known to prolong the QT interval.
- n. Patient has a history of torsades de pointes, congenital long QT syndrome, bradyarrhythmias, or uncompensated heart failure.
- o. Patient has evidence of hepatic impairment, as indicated by the following:

- aspartate aminotransferase (AST) or alanine aminotransferase (ALT) $>2.5 \times$ the upper limit of the normal range (ULN) at screening
- alkaline phosphatase (ALP) or total bilirubin $>2 \times$ ULN at screening

Note: Patients with Gilbert’s syndrome are eligible to participate if approved by the medical monitor.

Note: Patients with abnormalities in 2 or more of the following clinical laboratory parameters must be approved for enrollment by the medical monitor: AST, ALT, ALP, and total bilirubin.

- p. Patient has evidence of clinically significant renal impairment, indicated by a serum creatinine $>1.5 \times$ ULN at screening.
- q. Patient has received a monoamine oxidase inhibitor within 14 days of the baseline visit.
- r. Patient has a known allergy to any of the components of the IMP product.
- s. Patient has participated in an investigational drug or device study and received IMP/intervention within 30 days or 5 drug half-lives of baseline, whichever is longer.
- t. Patient is a pregnant or lactating female or plans to be pregnant during the study.
- u. Patient has a history of or acknowledges alcohol-related disorder in the previous 12 months, as defined in the DSM-V™.
- v. Patient has a positive urine drug screen test result or is unable to refrain from substance abuse throughout the study.

Statistical Considerations

Sample Size Rationale: It is estimated that approximately 50 patients per arm will enable a power of at least 90% to detect a beneficial standardized effect of 68% or more when the TEV-50717 arm is compared to placebo (difference of 6.5 in the change from baseline to week 8 in TTS, assuming a standard deviation of 9.5 in each arm) in a 2-sided type I error rate of 5% after accounting for potential dropouts.

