Safety Analyses: All adverse events will be coded using the Medical Dictionary for Regulatory Activities. Each patient will be counted only once in each preferred term or system organ class category for the analyses of safety. Summaries will be presented for all adverse events, adverse events determined by the investigator to be related to study treatment, serious adverse events, and adverse events causing withdrawal from the study. Summaries will be presented by treatment group and for all patients. Patient listings of serious adverse events and adverse events leading to withdrawal will be presented.

Observed values and changes from baseline in laboratory results and vital signs will be summarized descriptively.

Observed values in ECG parameters will be summarized, and counts and percentages of abnormal findings will be presented. In addition, the number and percentage of patients with on-treatment QTcF values > 450 , > 480 , or > 500 msec and change from baseline > 30 or > 60 msec will be presented.

The use of concomitant medications will be summarized by therapeutic class using descriptive statistics. Concomitant medications will include all medications taken while the patient is treated with IMP.

Observed values in the C-SSRS and observed values and changes from baseline in the CDI-2 (Parent and Self-report Profiles) will be presented by treatment group for all patients.

Sensitivity Analysis: Sensitivity analyses of primary and key secondary endpoints will be conducted using the per-protocol analysis set. Sensitivity analyses for missing data and the statistical model will be provided in the statistical analysis plan.

TABLE OF CONTENTS

TITLE PAGE	1
AMENDMENT HISTORY	2
INVESTIGATOR AGREEMENT.....	3
SPONSOR PROTOCOL APPROVAL	4
COORDINATING INVESTIGATOR AGREEMENT	5
COORDINATING INVESTIGATOR AGREEMENT	6
CLINICAL LABORATORIES AND OTHER DEPARTMENTS AND INSTITUTIONS	7
CLINICAL STUDY PROTOCOL SYNOPSIS.....	10
LIST OF ABBREVIATIONS.....	31
1. INTRODUCTION AND BACKGROUND INFORMATION	35
1.1. Introduction.....	35
1.2. Name and Description of Investigational Product.....	36
1.3. Findings from Nonclinical and Clinical Studies.....	36
1.3.1. Nonclinical Studies.....	36
1.3.1.1. Nonclinical Pharmacology.....	36
1.3.1.2. Nonclinical Pharmacokinetics and Drug Metabolism	37
1.3.1.3. Toxicology	37
1.3.2. Clinical Studies.....	38
1.3.2.1. Clinical Pharmacology Studies.....	38
1.3.2.2. Clinical Safety and Efficacy Studies	39

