9.7.1. Safety Analysis

All adverse events will be coded using the Medical Dictionary for Regulatory Activities. Each patient will be counted only once in each preferred term or system organ class category for the analyses of safety. Summaries will be presented for all adverse events, adverse events determined by the investigator to be related to study treatment, serious adverse events, and adverse events causing withdrawal from the study. Summaries will be presented by treatment group and for all patients. Patient listings of serious adverse events and adverse events leading to withdrawal will be presented.

Observed values and changes from baseline in laboratory results and vital signs will be summarized descriptively.

Observed values in ECG parameters will be summarized, and counts and percentages of abnormal findings will be presented. In addition, the number and percentage of patients with

on-treatment QTcF values >450, >480, or >500 msec and change from baseline >30 or >60 msec, will be presented.

The use of concomitant medications will be summarized by therapeutic class using descriptive statistics. Concomitant medications will include all medications taken while the patient is treated with IMP.

Observed values in the C-SSRS and observed values and changes from baseline in the CDI-2 (Parent and Self-report Profiles) will be presented by treatment group for all patients.

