**Statistical Analysis Plan for Interventional Studies**

Sponsor: Teva Branded Pharmaceutical Products R&D, Inc./Nuvelution TS Pharma, INC.;  
Protocol No.: TV50717-CNS-30060

---

Observed results of each ECG parameter and change from baseline will be summarized by treatment and overall, and by visit using descriptive statistics.

In addition, for QTcF, average baseline confirmed QTcF (the average of the screening and Day 1 QTcF), and the change from average baseline will be summarized by treatment and overall, and by visit using descriptive statistics.

QTcF values will be classified as having QTc prolongation according to the following conditions.

QTc Prolongation
Confirmed QTcF >450 msec
Confirmed QTcF >480 msec
Confirmed QTcF >500 msec
Increase from baseline QTcF $\geq$ 60 msec
Increase from average baseline confirmed QTcF $\geq$ 60 msec
Increase from baseline QTcF $\geq$ 30 msec
Increase from average baseline confirmed QTcF $\geq$ 30 msec

The number and percentage of patients with QTc prolongation will be summarized by treatment and overall, and by visit.

A shift table comparing the overall ECG assessment from baseline to each visit will be presented.

In addition, the abnormal post-baseline ECG results will also be summarized for patients with at least one abnormal value during the treatment period. The summary will be completed by treatment and overall, and age groups (6 - < 8 years, 8 - < 12 years, and 12 - < 16 years), and overall using the age at the time of the individual assessment.

Criteria for abnormal values used in the study are presented in [Table 6](#).

This document is confidential.

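### The QTcF >450 msec row of the QTc prolongation summary has no pre-treatment condition, so it counts unchanged values that the entry criteria admit; the effect is small and descriptive

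*Protocol*

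**What the plan says.** Exclusion m (synopsis and Protocol 4.2) excludes a child whose screening QTcF is ">450 msec (males) or >460 msec (females), or >480 msec (with right bundle branch block"). It does not refer to the day-1 ECG, although Protocol Table 2 schedules one.

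For reporting, the synopsis and Protocol 9.7.1 use one set of limits for everyone. The synopsis asks for "the number and percentage of patients with on-treatment QTcF values > 450 , > 480 , or > 500 msec", and Protocol 9.7.1 for "on-treatment QTcF values >450, >480, or >500 msec and change from baseline >30 or >60 msec". SAP 9.9 introduces its list with "QTcF values will be classified as having QTc prolongation according to the following conditions". The first row is "Confirmed QTcF >450 msec", followed by >480 and >500 msec. Increases of at least 30 and at least 60 msec have their own rows, measured once from baseline and once from the average of the screening and day-1 values. The SAP then says: "The number and percentage of patients with QTc prolongation will be summarized by treatment and overall, and by visit". The population is the whole safety analysis set.

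No legible text attaches a sex, bundle-branch or pre-treatment condition to the absolute rows. In SAP 9.9 the term confirmed refers to averaging repeat ECGs at a visit; it says nothing about the value before treatment. The ECG shift table in SAP 9.9 uses the overall Normal/Abnormal reading, and SAP Table 6 covers heart rate, PR and QRS only.

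**The concern.** The reporting limit of 450 msec is lower than two of the three entry limits. A child may therefore enter above 450, stay exactly there, and appear in a row whose label suggests something that happened on treatment.

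Elsewhere the plan does compare with the pre-treatment state. SAP Table 5 requires both an absolute value and a change from baseline before supine or standing blood pressure or pulse is called markedly abnormal. SAP 9.4 counts an adverse event as treatment-emergent only if it begins or worsens after the first dose. SAP 9.9 already derives an average pre-treatment QTcF but uses it only for changes.

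What is at stake is how a small safety count is read. With 50 children per arm, one child is 1/50 = 2 percentage points. The row alone does not show whether a counted child arrived that way.

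**Working it through.** The documents state no figure on this point, so there is none to reproduce. Two checks apply.

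**1. Do the rules admit and then count an unchanged child?** Take children whose QTcF is the same before and during treatment, apply exclusion m, then the rows of SAP 9.9.

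| Child, QTcF unchanged | Entry limit | Admitted | >450 | >480 | >500 | Any increase row |
|---|---|---|---|---|---|---|
| Boy, 450 | 450 | yes | no | no | no | no |
| Girl, 455 | 460 | yes | **yes** | no | no | no |
| Girl, 460 | 460 | yes | **yes** | no | no | no |
| Right bundle branch block, 475 | 480 | yes | **yes** | no | no | no |
| Right bundle branch block, 480 | 480 | yes | **yes** | no | no | no |

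Four of the five are counted as prolonged with zero change. If the >450 row also required a pre-treatment value of at most 450, none of those four would be counted. No admitted screening value exceeds 480, so the entry limits cannot put an unchanged child into the >480 or >500 rows.

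**2. How many children could this be?** The documents give no QTcF mean, spread or share of girls, so all inputs here are assumptions:

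- mean QTcF m of 405 to 420 msec, with girls 5 msec higher;
- between-child SD of 15 to 18;
- within-child (visit-to-visit) SD of 8 to 12;
- 20% to 30% girls;
- no drug effect and no right bundle branch block patients.

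Model: QTcF at a visit = child mean + independent visit error. A child is kept if the screening value is at most 450 (boys) or 460 (girls). A child is counted if week 4 or week 8 exceeds 450. The run used 24 combinations (m at 405, the midpoint and 420; both ends of the other ranges) with 1 million children each, scaled to 150.

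| Quantity, of 150 children | Range | Share of those counted |
|---|---|---|
| Counted above 450 at week 4 or 8 | 1.1 to 16.0 | – |
| Counted, with screening or day-1 value above 450 | 0.3 to 5.9 | 19% to 45% |
| Counted, with (screening + day 1)/2 above 450 | 0.1 to 3.0 | 7% to 27% |
| Counted, with screening value above 450 | 0.1 to 2.0 | 5% to 19% |

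The third line matches the average that SAP 9.9 already derives, so it is the relevant size. Per arm the upper end is 3.0/3 = 1.0 child, or 1.0/50 = 2 percentage points. The second line is larger because a single noisy day-1 reading is enough. A child at 440 and then 455 averages (440 + 455)/2 = 447.5 and is not above 450 on the average.

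**The case against.** The strongest reply is that the plan already reports change. The protocol sentence goes on to "change from baseline > 30 or > 60 msec will be presented", and SAP 9.9 has four increase rows plus by-visit summaries of QTcF and its change from both baselines. The girl unchanged at 455 appears in none of the increase rows. Absolute rows describe values reached, increase rows describe change, and reporting both is legitimate. This stands as a defence of keeping the all-patient rows. It does not answer the point, because the increase rows are separate counts and do not show which children above 450 were above it before treatment. If the by-visit table includes baseline, it would give only a separate total for that visit, without linking children across visits.

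Second, SAP 6.1 puts all visit data in patient listings, so a diligent reader could trace each child. That is true, and it rules out saying that the report as a whole hides the information. The summary row still does not show it. The SAP's index of tables is redacted, so a QTcF category table cannot be excluded, but the legible text of SAP 9.9 does not describe one.

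Third, a reader might infer that the row could create or conceal a drug signal. The documents do not support this. The arms are randomized with a concurrent placebo group, so children with high entry values are balanced in expectation. No test or decision rule is attached to the row, and the protocol's QTcF rule for stopping study drug uses >500 msec or an increase >60 msec. What remains is chance imbalance in a small count.

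Fourth, one might take 5.9 of 150 (or 45%) as the size, or extend the point to all three absolute rows. The first counts any single pre-treatment reading above 450, much of it visit-to-visit noise. The second fails because the entry limits stop at 480.

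**Conclusion.** The point holds for the >450 row. SAP 9.9 labels as QTc prolongation a count that includes unchanged values the entry criteria admit, and no summary in the legible plan separates them from new exceedances.

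The size is about 0.1 to 3.0 of 150 children, or 7% to 27% of those counted. It rests entirely on the assumed distributions above. The frequency of right bundle branch block is unknown and is not included; such a patient admitted well above 450 would almost certainly be counted.

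The consequence is descriptive: noise in a small count, no systematic bias between arms, and no effect on efficacy results. This is a cheap improvement in presentation and does not threaten the safety conclusions.

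**What to change.** In SAP 9.9, keep the all-patient counts for >450, >480 and >500 msec as planned, and add one of the following.

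- Beside the >450 row, the number of children with a new exceedance: post-baseline QTcF >450 with the average of screening and day 1 at most 450. The denominator is the children whose pre-treatment average is at most 450.
- A table by treatment group of pre-treatment QTcF category (≤450, >450–480, >480–500, >500) by worst on-treatment category, using the same pre-treatment average.

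Both use ECGs already scheduled and an average the SAP already derives. The cost is a short SAP wording change, one extra row or table, and, for the first option, a denominator slightly different from the rest of the summary. Entry limits, dosing and stopping rules are untouched. The change should be made before unblinding.
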